[figure not shown]

AMEPAROMO CAPSULES 250 mg Drug Use Investigation
NON-INTERVENTIONAL (NI) STUDY PROTOCOL

090177e1918e8906\Approved\Approved On: 26-Jul-2019 07:04 (GMT)

STUDY INFORMATION

| | |
|---|--|
| Title | AMEPAROMO Capsules 250 mg Drug Use Investigation |
| Protocol ID | B3391001 |
| Protocol version identifier | 2 |
| Date of last version of protocol | 27 APR 2015 |
| Active substance | Paromomycin sulfate |
| Medicinal product | AMEPAROMO Capsules 250 mg |
| Research question and objectives | This study will be conducted to investigate the safety and effectiveness of AMEPAROMO Capsules 250 mg in daily medical practice in terms of: 1) Adverse reactions unexpected from precautions (unknown adverse reactions); 2) Occurrence of adverse reactions under daily medical practice; and 3) Factors that may affect safety, effectiveness and other relevant matters. |
| Author | PPD Post Marketing Study Strategy and Management PPD |

090177e1918e8906\Approved\Approved On: 26-Jul-2019 07:04 (GMT)

TABLE OF CONTENTS

| | |
|---|----|
| 1. LIST OF ABBREVIATIONS..... | 4 |
| 2. RESPONSIBLE PARTIES..... | 4 |
| 3. AMENDMENTS AND UPDATES..... | 4 |
| 4. MILESTONES..... | 4 |
| 5. RATIONALE AND BACKGROUND..... | 4 |
| 6. RESEARCH QUESTION AND OBJECTIVES | 5 |
| 7. RESEARCH METHODS | 6 |
| 7.1. Study design | 6 |
| 7.2. Setting..... | 6 |
| 7.2.1. Inclusion criteria | 6 |
| 7.2.2. Exclusion criteria | 6 |
| 7.2.3. Sites for this study | 6 |
| 7.2.4. Planned investigation period..... | 7 |
| 7.2.5. Study methods | 7 |
| 7.2.6. Observation period..... | 7 |
| 7.3. Variables..... | 8 |
| 7.3.1. Background..... | 8 |
| 7.3.2. Targeted drug use record | 9 |
| 7.3.3. Concomitant therapy..... | 10 |
| 7.3.4. Study discontinuation record | 10 |
| 7.3.5. Effectiveness evaluation | 10 |
| 7.3.6. Adverse events..... | 11 |
| 7.3.7. Major investigation items | 12 |
| 7.4. Data sources | 12 |
| 7.5. Study size | 12 |
| 7.5.1. Planned sample size..... | 12 |
| 7.5.2. Rationale for sample size..... | 12 |
| 7.6. Data management..... | 12 |
| 7.6.1. Data collection method | 12 |
| 7.6.2. Patient registration..... | 12 |

| | |
|---|-----------|
| 7.6.3. Reminders concerning completion, revision, and submission of case report form..... | 13 |
| 7.7. Data analysis | 13 |
| 7.8. Quality control..... | 14 |
| 7.9. Limitations of the research methods | 14 |
| 7.10. Other aspects | 14 |
| 8. PROTECTION OF HUMAN SUBJECTS | 14 |
| 8.1. Patient information and consent..... | 14 |

1. LIST OF ABBREVIATIONS

| Abbreviation | Definition |
|--------------|----------------------------------|
| AE | Adverse event |
| EDP | Exposure during pregnancy |
| IEC | Independent Ethics Committee |
| IRB | Institutional review board |
| N/A | Not applicable |
| NIS | Non-interventional study |
| SRSD | Single Reference Safety Document |

3. AMENDMENTS AND UPDATES

| Amend ment number | Date | Substantial or administrative amendment | Protocol section(s) changed | Summary of amendment(s) | Reason |
|-------------------|--------------|---|-----------------------------|--|--|
| Version 2 | 02 June 2016 | Other amendment(s) | 12 | Changes in the contents of outsourced activities | Because the contents of outsourced activities were changed |

4. MILESTONES

| Milestone | Planned date |
|--------------------------|---|
| Start of data collection | May 2015 |
| End of data collection | Until the target sample size is achieved or one year prior to the reexamination period after the start of the study, whichever is earlier |
| Final study report | To be decided |

5. RATIONALE AND BACKGROUND

AMEPAROMO (nonproprietary name, paromomycin sulfate) has been positioned as one of the standard drugs for the treatment of intestinal amebiasis in Japanese and overseas guidelines because it is rarely absorbed by

the digestive tract following oral administration and thus can act on *Entamoeba histolytica* (protozoa and cysts) in the intestinal lumen at high concentrations. In Japan, paromomycin preparations were approved and distributed for the indications including Shigellosis during a period from the 1960's to 1990's, but thereafter, because the approval was withdrawn, drugs, which were normally used in foreign countries, were not available in Japan. As its countermeasure, the current "Study on the establishment of medical responses through optimal treatments with orphan drugs for imported tropical diseases and infestations" Group (Research Group of Tropical Diseases and Parasitic Diseases) has taken the responsibility to import paromomycin preparations since 1998 to organize a system paying consideration that these drugs can be available for the treatment of patients with amebiasis. Under these circumstances, the Japanese Association for Infectious Diseases and the Research Group of Tropical Diseases and Parasitic Diseases submitted a request for the development of paromomycin preparations for the indication of intestinal amebiasis in Japan, and it was reviewed by the "Evaluation Committee on Unapproved or Off-labeled Drugs with High Medical Needs," Ministry of Health, Labour and Welfare (MHLW). In December 2010, in response to the development request from the MHLW, Pfizer Japan Inc. undertook the development of "AMEPAROMO Capsules 250 mg," and approval was granted to the indication, "intestinal amebiasis," in December 2012.

In foreign countries, a paromomycin preparation has been sold by Parke-Davis GmbH (current Pfizer Inc.) in Germany since 1961 and approved and distributed in 18 countries including the EU countries as of August 2012.

The drug use investigation of AMEPAROMO Capsules 250 mg (hereinafter referred to as "this study") shall be conducted to collect or confirm information on the occurrence by type of adverse reaction associated with AMEPAROMO in daily medical practice, and information on the quality, effectiveness and safety of AMEPAROMO. The information collected from this study shall be used to provide proper use information and prepare documents for the reexamination application. This study shall be therefore implemented in strict compliance with the "MHLW Ordinance on the Standard for Post-Marketing Studies and Clinical Trials of Medical Products" (MHLW Ordinance No. 171 dated December 20, 2004). Data obtained from the patients registered in this study will be reported to the MHLW pursuant to the Pharmaceutical Affairs Law; pertinent to which, data may be publicly posted in the MHLW's "Pharmaceuticals and Medical Devices Safety Information" and "Pharmaceuticals and Medical Devices Information Website (<http://www.info.pmda.go.jp>)" as a listing of patients with adverse reactions, which will present the names of drugs, adverse reactions, sex, age (increment of 10 years), and other relevant information. Furthermore, data collected may also be disclosed if the MHLW is required to disclose such information in accordance with the "Act on Access to Information Held by Administrative Organs" (Law No. 42 dated May 14, 1999) provided that in no event will the names of physicians, medical institutions, and other personal information be subject to such disclosure, nor will it be posted or disclosed in any form or shape.

6. RESEARCH QUESTION AND OBJECTIVES

AMEPAROMO Capsules 250 mg (hereinafter referred to as "AMEPAROMO") have been distributed over 50 years in foreign countries and demonstrated a high safety profile. Also, it was sold over 20 years in Japan. Furthermore, AMEPAROMO is a drug rarely absorbed by the intestinal tract and causes very few adverse reactions that are concerned for aminoglycoside antibiotics. Its use is recommended for the prevention of recurrence in textbooks and guidelines worldwide.

The safety and effectiveness of AMEPAROMO have been evaluated in Japanese subjects, and it has been assessed as effective with no special safety concern as a drug for the treatment of intestinal amebiasis.

The evaluation of AMEPAROMO in Japan was, however, made in limited patients performed as a group research by the Research Group of Tropical Diseases and Parasitic Diseases. In addition, the number of patients with intestinal amebiasis targeted by AMEPAROMO is extremely limited so that medical institutions where treatment is actually given after marketing are also assumed to be limited.

In the light of these, this study will be mainly requested to institutions having the results of AMEPAROMO treatment and will collect the additional effectiveness and safety evidence of AMEPAROMO under actual conditions of use after marketing by specifying criteria.

This study will investigate the safety and effectiveness of AMEPAROMO in daily medical practice in terms of: 1) Adverse reactions unexpected from precautions (unknown adverse reactions); 2) Occurrence of adverse reactions under daily medical practice; and 3) Factors that may affect safety, effectiveness and other relevant matters.

7. RESEARCH METHODS

7.1. Study design

This study is a multicenter open-label study conducted in patients receiving AMEPAROMO, for which case report forms (CRFs) will be recorded based on data presented in medical records obtained in daily medical practice.

7.2. Setting

Patients who satisfy all of the inclusion criteria are subject to this study.

7.2.1. Inclusion criteria

Patients who have never been treated with AMEPAROMO

The indication, dosage and administration of AMEPAROMO are as mentioned below. See the latest package insert when using AMEPAROMO.

INDICATION

Intestinal amebiasis

[PRECAUTIONS CONCERNING INDICATIONS]

AMEPAROMO should not be used for the treatment of parenteral amebiasis because AMEPAROMO acts only on protozoa and cysts in the intestine.

DOSAGE AND ADMINISTRATION

The usual dosage for adults is 1500 mg (potency) of paromomycin sulfate administered orally after meals, divided into 3 doses per day for 10 days.

7.2.2. Exclusion criteria

There are no exclusion criteria for this study.

7.2.3. Sites for this study

This study will be implemented at 20 to 30 sites including the department of infectious diseases and department of internal medicine.

090177e1918e8906\Approved\Approved On: 26-Jul-2019 07:04 (GMT)

7.2.4. Planned investigation period

This study will be conducted during the following period:

Investigation period: From May 2015 until the target sample size is achieved or one year prior to the reexamination period after the start of the study, whichever is earlier

Registration period: From May 2015 until the target sample size is achieved or one year and 3 months prior to the reexamination period after the start of the study, whichever is earlier.

7.2.5. Study methods

7.2.5.1. Study system

This study will be implemented using a central registration system.

7.2.6. Observation period

The observation period shall start on the day the treatment with AMEPAROMO begins (Day 1) and end on Day 10 during which patient background information, records on AMEPAROMO treatment, records on concomitant therapies, and records on the treatment status and discontinuation of AMEPAROMO shall be entered in CRFs. When the treatment is discontinued during the observation period, the observation period shall be until the day when AMEPAROMO treatment is discontinued.

7.3. Variables

The investigator will conduct this study in accordance with the following variables/schedule of observation.

Table 1. Variables/schedule of observation

| Variables | | Timing | Registration Form | CRF | | |
|------------------------------|---|--------|-----------------------------|-------------------------|----------------------------------|---|
| | | | At the time of registration | Initiation of treatment | Completion of observation period | Up to 3 months after the completion of observation period |
| Background | ID number | | • | | | |
| | Sex | | • | | | |
| | Age on the start date of AMEPAROMO treatment | | • | | | |
| | Enrollment criterion | | • | | | |
| | Start date of AMEPAROMO treatment | | • | | | |
| | Targeted disease | | | • | | |
| | Hospitalization status (inpatient/outpatient) | | | • | | |
| | Body height | | | • | | |
| | Body weight | | | • | | |
| | Medical history | | | • | | |
| | Records on previous treatment drugs | | | • | | |
| | Pregnancy status [female only] | | | | • | |
| Targeted drug use record | | | | • | • | |
| Concomitant therapy | | | | ←————→ | | |
| Study discontinuation record | | | | | • | |
| Effectiveness evaluation | Examination of cysts after AMEPAROMO treatment | | | | ←————→ | |
| | Clinical response to AMEPAROMO (assessed by the investigator) | | | | ←————→ | |
| Adverse events | | | | ←————→ | | |

7.3.1. Background

(1) Input the information on the start day of treatment with AMEPAROMO.

[1] ID number

[2] Sex

[3] Age on the start date of AMEPAROMO treatment

- [4] Start date of AMEPAROMO treatment
- [5] Body height
- [6] Body weight
- [7] Targeted disease
 - Name of disease
 - Severity
 - Initial onset or recurrence
- [8] Hospitalization status (inpatient/outpatient)
- [9] Medical history (information except for the targeted disease)
 - Presence or absence of human immunodeficiency virus (HIV) infection
 - Name of disease or syndrome other than the aboveBy history or complication*
*Enter chronic diseases (including allergies), diseases requiring treatment, diseases or impairment accompanying surgery, inpatient treatment or sequelae, and the names of diseases or syndromes that may be other problems. If these were cured prior to AMEPAROMO treatment, they are “history,” and if such diseases, etc. still persist at the time of treatment, they are “complications.”
- [10] Records on previous treatment drugs for intestinal amebiasis
 - Name of drug (product name)
 - Route of administration
 - Daily dose
 - Treatment period
 - Effectiveness evaluation

(2) Input the following information during a period from the start day of AMEPAROMO treatment to the end day of the observation period or the day of treatment discontinuation:

- Pregnancy status and date of delivery/expected date (female only)

7.3.2. Targeted drug use record

Input the following information for the targeted drug:

- [1] Dose
- [2] Frequency of doses per day
- [3] Treatment period

7.3.3. Concomitant therapy

7.3.3.1. Drug therapy

Input the following information on all drugs used during the observation period. If adverse events (AEs) occurred, drugs administered for the treatment of AEs will be also entered:

- [1] Name of drug (product name)
- [2] Route of administration
- [3] Treatment period
- [4] Presence or absence of treatment for AEs

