7.3.4. Study discontinuation record

Whether or not AMEPAROMO treatment could be completed should be checked. If AMEPAROMO treatment could not be completed, the date of the final observation should be entered, and the main reason for discontinuation corresponding to the items below should be chosen and documented. If an AE is selected for the reason, detailed information should be recorded in the AE column.

- [Reason for discontinuation]
- Insufficient clinical response
 - AEs
 - Not making revisits
 - Hospital/department transfer
 - Others

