7.3.5. Effectiveness evaluation

[1] Examination of cysts after AMEPAROMO treatment

After the completion of the observation period (or treatment discontinuation), an examination of cysts will be carried out, and the result should be recorded. The result of cyst examination shall be within 3 months after the end day of the observation period (or day of treatment discontinuation)

- Examination performed
 - Date of sample collection
 - Result of cyst examination: Negative, positive or indeterminate

- Examination not performed

[2] Clinical response to AMEPAROMO (assessed by the investigator)

After the completion of the observation period (or treatment discontinuation), the clinical response to AMEPAROMO should be comprehensively assessed based on the course of the general condition, laboratory findings and other relevant data after the start of AMEPAROMO treatment, and the results should be recorded:

- Effective
- Not effective
- Indeterminate (The reason should be recorded.)

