5.2.1. Cyst Analysis Set

The cyst analysis set consists of the patients in the safety analysis set who have undergone the examination of cysts after AMEPAROMO treatment. Patients who meet any of the following criteria will be excluded:

- g. Examination of cysts has not been performed (description in the report, “no information on examination of cysts”)

- h. Non-target disease of the study (description in the report, “Non-target disease of the study”) [That is, “others” is checked with no other information in the CRF item that asks the disease (diagnosis) that required the use of AMEPAROMO.]

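### A cyst-negative result obtained after another or repeat anti-amebic course counts as an AMEPAROMO success, and recording of such courses up to the cyst sample is not assured

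*Protocol*

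**What the plan says.** **Drug records.** Protocol 7.3.3.1 says "Input the following information on all drugs used during the observation period". It then adds "If adverse events (AEs) occurred, drugs administered for the treatment of AEs will be also entered", without an end date for that addition. Protocol 7.2.6 fixes the period: "The observation period shall start on the day the treatment with AMEPAROMO begins (Day 1) and end on Day 10"; after an early stop, "the observation period shall be until the day when AMEPAROMO treatment is discontinued".

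**Cyst result.** Protocol 7.3.5 says "The result of cyst examination shall be within 3 months after the end day of the observation period (or day of treatment discontinuation". Protocol 7.7 and SAP 2.1 make the proportion of cyst negative the main effectiveness item.

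**Counting rule.** Under SAP 5.2.1 the cyst analysis set "consists of the patients in the safety analysis set who have undergone the examination of cysts after AMEPAROMO treatment". The only further exclusions are no cyst examination and non-target disease. SAP 8.2.4.1 divides negatives by negatives plus positives, with a 95% interval that SAP 8.1.3 makes exact. SAP 7 says only that missing effectiveness data are not imputed.

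**Discontinuation.** Protocol 7.3.4 lists "Insufficient clinical response" as a reason for stopping. No effectiveness rule in the SAP uses it.

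**The concern.** Routine drug recording closes at about the point where the window for the cyst sample opens. Take a patient who stops early for lack of response, or who completes 10 days and remains unwell, then receives another anti-amebic drug and tests negative weeks later. If that negative is the result entered, the patient is in the numerator, although the clearance may be due to the later drug.

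This matters because the study has no control group (Protocol 7.9) and its results support the reexamination application (Protocol 5, SAP 3). The proportion of cyst negative therefore stands largely on its own, and the patients affected are those in whom AMEPAROMO alone may have failed.

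**Working it through.** The plan has no figure to reproduce. The sample size of 100 is a feasibility choice without a formula (Protocol 7.5.2), and no clearance or switching rate is given. The check compares the time windows and the counting rules, then works out the effect per patient.

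**Step 1. Windows, for a patient who completes on Day 10**

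| Record | Runs to | Source |
|---|---|---|
| Routine concomitant drugs | Day 10 | Protocol 7.2.6, 7.3.3.1 |
| Adverse events confirmed for the CRF | end of observation, Day 10 | Protocol 7.3.6 |
| Safety reporting, including lack of efficacy | at least 28 days after the last dose, so at least Day 10 + 28 = Day 38 if the last dose is on Day 10 | Protocol 9.1, 9.2 |
| Cyst sample | up to 3 months after Day 10 | Protocol 7.3.5 |

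Even the longest of the record windows need not reach the latest permitted sample date.

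**Step 2. Counting rule.** I looked for any rule that would separate a patient given another anti-amebic course before the sample. SAP 5.2.1, 7 and 8.2.4.1 contain none. The effectiveness factors in SAP 5.3 leave out concomitant medication, although the safety factors include it. Even a fully recorded switch would therefore leave the main count unchanged.

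**Step 3. Effect per patient.** Let n be the patients with a positive or negative result, x the recorded negatives, and k those negative only after another or repeat course.

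- SAP as written: x/n
- Those k kept in the denominator but not counted as negative: (x − k)/n
- Difference: k/n. For k = 1 this is 1/100 = 1 percentage point at n = 100 and 1/50 = 2 points at n = 50.

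**Step 4. Illustration.** Assumed, not from the documents: 90% recorded negative, and k = 2, 5 or 10. Intervals are exact 95%.

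| n | k | SAP as written | Not counted as negative |
|---|---|---|---|
| 100 | 2 | 90.0% (82.4 to 95.1) | 88.0% (80.0 to 93.6) |
| 100 | 5 | 90.0% (82.4 to 95.1) | 85.0% (76.5 to 91.4) |
| 100 | 10 | 90.0% (82.4 to 95.1) | 80.0% (70.8 to 87.3) |
| 50 | 2 | 90.0% (78.2 to 96.7) | 86.0% (73.3 to 94.2) |
| 50 | 5 | 90.0% (78.2 to 96.7) | 80.0% (66.3 to 90.0) |
| 50 | 10 | 90.0% (78.2 to 96.7) | 70.0% (55.4 to 82.1) |

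Dropping these patients altogether is a different analysis and moves the figure much less. At n = 100 and k = 5 it gives 85/95 = 89.5% (81.5 to 94.8). A supplementary analysis must therefore say which it does.

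**The case against.** A reader might infer that a replacement drug is never recorded, so that the error cannot be corrected at analysis. The documents do not support that.

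- Drugs given to treat adverse events are also entered, with treatment period and no stated end date (Protocol 7.3.3.1). Lack of efficacy and worsening of the underlying disease are listed as examples of adverse events (9.4.1). Lack of efficacy goes on both the CRF and the NIS AE Report Form (9.1), with relevant concomitant medications. Reporting runs to at least 28 days after the last dose (9.2). An early stop for insufficient response is the case most likely to be caught.
- A drug started on the day of discontinuation may fall inside the observation period (7.2.6).
- AMEPAROMO has its own treatment-period record (7.3.2) with no Day 10 limit. SAP 5.3 and 8.2.2 expect durations beyond 10 days, so a repeat course might appear there.
- SAP 8.2.1 and 8.2.2 tabulate discontinuation reasons and concomitant medication in the effectiveness sets. The investigator's clinical response is a second reported measure.
- The miscount needs the later negative to be the result entered. Protocol 7.3.5 does not say which result counts if there are several, and a positive that prompted the switch could be the one recorded.
- The study is exploratory (SAP 4.1), and Protocol 7.9 already discloses confounding and missing information.

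All of this stands as qualification. It does not remove the point. A switch that comes after the reporting period, or that the investigator does not report as lack of efficacy, need not be recorded. The tabulations are not crossed with the cyst result. Clinical response is a separate endpoint and leaves the main item unchanged. The general limitations do not mention later treatment.

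**Conclusion.** The point holds and should be addressed. Routine drug recording stops up to 3 months before the latest permitted cyst sample, other routes capture some later courses but not all, and no SAP rule uses any of them for the main effectiveness item.

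The size is 1/n per affected patient, in the drug's favour. This rests on two assumptions: that the later negative is the result recorded, and that the comparison is with not counting that patient as negative. Some of these patients might have cleared on AMEPAROMO alone, so the recount is a cautious figure and not a corrected truth.

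Two further inferences go too far. One is a particular total inflation: with no switching rate in the documents, the table above is illustration only. The other is that every patient stopped for insufficient response is a failure: such a patient can test negative without any other drug.

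**What to change.** 1. **Protocol 7.3.3.1 and CRF.** Record any anti-amebic drug, including a repeat AMEPAROMO course, with start and end dates, up to the date of the cyst sample. Use a query for forms already submitted.
2. **SAP 8.2.4.1.** Keep the main figure. Add a supplementary proportion, with exact 95% interval, in which a negative obtained after another or repeat anti-amebic course stays in the denominator but is not counted as negative.
3. **SAP, from data already collected.** Cross-tabulate cyst result by discontinuation for "Insufficient clinical response". A version counting those patients as not negative may be shown only as a labelled lower bound. The label should say that it can override true laboratory negatives and does not cover completers who later switched.

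An optional, separate addition is concomitant anti-amebic drug during the observation period as an effectiveness factor in SAP 5.3. The rule in SAP 8.1.3 on subgroups under 10 may suppress the comparison.

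Cost: one chart-derived CRF item, some queries (the CRFs are handwritten and the SAP history describes the study as ongoing), SAP wording, and a supplementary figure that may be less favourable. Item 3 needs no new data. The change concerns recording and analysis only and alters no patient's care.

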5.3. Subgroups

Subgroup analyses of safety will be performed for the following patient background factors. Underlined categories will be used as a reference in comparisons between subgroups.

- Sex [male, female]
- Children (<15 years), adults (≥15 to <65 years), elderly (≥65 years)
- Inpatient/outpatient status at the first prescription [inpatient, outpatient]
- Diagnostic name [intestinal amebiasis, others]
- Severity [mild, moderate, severe, unknown]
- Initial onset/recurrence [initial onset, recurrence]
- HIV infection [absent, present]
- Past medical history other than HIV infection [absent, present]
- Concurrent illness other than HIV infection [absent, present]
- Presence or absence of prior treatment for intestinal amebiasis [absent, present]
- Presence or absence of hepatic dysfunction [absent, present]
- Presence or absence of renal dysfunction [absent, present]
- Presence or absence of concomitant medication up to the development of adverse drug reactions^a [absent, present]

Subgroup analyses of safety will be performed for the other factors shown below.

- Pregnant and parturient women (pregnancy present)

^a: The presence or absence of concomitant medications will be determined by excluding concomitant medications started to be used after the day of onset of the last adverse drug reaction observed during the observation period plus 28 days.

- Overdose^b (overdose present)

Patients in whom AMEPAROMO might have been contraindicated per the package insert (hereinafter referred to as contraindicated patients) will be sampled from the registry according to separately-specified criteria and be analyzed for the safety of AMEPAROMO as a subgroup analysis.

Subgroup analyses of effectiveness will be performed for the following patient background factors. Underlined categories will be used as a reference in comparisons between subgroups.

- Sex [male, female]
- Presence or absence of hepatic dysfunction [absent, present]
- Presence or absence of renal dysfunction [absent, present]
- Children (<15 years), adults (≥15 to <65 years), elderly (≥65 years)
- Severity [mild, moderate, severe, unknown]
- Initial onset/recurrence [initial onset, recurrence]
- HIV infection [absent, present]
- Past medical history other than HIV infection [absent, present]
- Concurrent illness other than HIV infection [absent, present]
- Presence or absence of prior treatment for intestinal amebiasis [absent, present]

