8.2.3. Safety Analysis

Safety will be analyzed using data collected during the observation period (from the start day of AMEPAROMO treatment to the end day of AMEPAROMO treatment) plus 28 days^d. All adverse events reported in the study will be included in listings.

^c: Because the dosage and administration of AMEPAROMO is “the usual dosage for adults is 1500 mg (potency) of paromomycin sulfate administered orally after meals, divided into 3 doses per day for 10 days”, overdose present was defined as “daily total dose exceeded 1500 mg on at least 1 day, or the duration of treatment is 12 days or more”. Only dose per single dose, number of doses, start day, and end day are collected as records on treatment with AMEPAROMO in the CRF. If AMEPAROMO is taken a total of 30 times in 10 days and the initial dose on the start day (Day 1) is given after lunch or supper, the last dose on the last day (Day 11) will be after breakfast or lunch. Because the duration of treatment from the start day to the end day is calculated to be 11 days in tabulation, the duration of treatment of 12 days or more was selected.

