8.2.3.5. Exploratory Analysis

The following exploratory analysis will be performed for factors affecting safety:

- For adverse drug reactions with high incidence ($> 10\%$), factors for development of adverse drug reactions will be examined using methods such as logistic regression analysis.
- To examine the effects of concomitant medications on development of adverse drug reactions, the number and proportion of patients by name of concomitant drug^c (drug subclassification and nonproprietary name) will be calculated by presence or absence of adverse drug reactions.

Additional exploratory analysis may be performed, as necessary. Among those exploratory analyses, only those that resulted in important interpretations will be reported.

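### Concomitant drugs are routinely recorded only to Day 10 or discontinuation, but the SAP relates drugs to reactions for 28 days after treatment, so later drug exposure is captured unequally between patients with and without reactions

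*Protocol*

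**What the plan says.** Collection. Protocol 7.3.3.1 states: "Input the following information on all drugs used during the observation period". It adds that if adverse events occurred, "drugs administered for the treatment of AEs will be also entered", with no end date. Protocol 7.2.6 defines the period: "The observation period shall start on the day the treatment with AMEPAROMO begins (Day 1) and end on Day 10". For a patient who stops early, "the observation period shall be until the day when AMEPAROMO treatment is discontinued". SAP 2.1 repeats the Day 10 end.

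Analysis window. SAP 8.2.3 begins: "Safety will be analyzed using data collected during the observation period (from the start day of AMEPAROMO treatment to the end day of AMEPAROMO treatment") and then adds 28 days. Its footnote d takes the 28 days from the reporting period of the NIS AE Report Form.

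Use of the drug data. SAP 5.3 lists concomitant medication, absent or present, as a safety subgroup factor. Footnote a leaves out only drugs begun "after the day of onset of the last adverse drug reaction observed during the observation period plus 28 days". SAP 8.2.3.5 adds a table by drug name and by presence or absence of reactions, with the stated aim: "To examine the effects of concomitant medications on development of adverse drug reactions". The same cut-off applies there.

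Other routes. Protocol 9 treats the NIS AE Report Form as part of the CRF. Protocol 9.1 requires concomitant medications to be supplied for serious and other 24-hour reportable events. Lack of efficacy is among these (9.1, 9.4.3). Non-serious adverse events go on the CRF but not on that form.

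**The concern.** The SAP treats a drug started in the 28 days after treatment, before a late reaction, as exposure. The CRF drug-therapy item does not ask for that drug. If the patient used nothing earlier, the two-level factor in SAP 5.3 puts the patient under 'absent'. There is no 'not collected' level, and SAP section 7 gives no rule for missing concomitant-drug data.

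What is at stake is an analysis that serves a stated objective, the factors that may affect safety. It compares patients with and without reactions, yet how much is known about later drugs depends on whether the patient had an event that triggered extra recording. According to the SAP's change history, version 3.0 both lengthened the safety window and added the concomitant-drug analyses. The protocol's amendment table lists only a change to section 12.

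**Working it through.** The plan states no figure on this point to reproduce. The check is window arithmetic followed by a trace of which drugs reach the data.

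**Inputs**
- Drug recording ends on Day 10, or on the day of discontinuation if earlier (Protocol 7.2.6, 7.3.3.1).
- The reaction window ends 28 days after the end of treatment (SAP 8.2.3).

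**Formula.** With treatment ending on Day k (k no more than 10), recording covers k days and the window ends on Day k + 28. Uncovered days = (k + 28) − k = 28. Uncovered share = 28/(k + 28).

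| Treatment ends | Window ends | Days without routine drug entry | Share |
|---|---|---|---|
| Day 3 | Day 31 | 28 | 28/31 = 90.3% |
| Day 5 | Day 33 | 28 | 28/33 = 84.8% |
| Day 7 | Day 35 | 28 | 28/35 = 80.0% |
| Day 10 | Day 38 | 28 | 28/38 = 73.7% |

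The SAP's overdose footnote describes a 30-dose course whose last dose falls on Day 11. Protocol recording then still ends on Day 10 and the SAP window ends on Day 11 + 28 = Day 39. That leaves 39 − 10 = 29 uncovered days, 29/39 = 74.4%. These are shares of calendar days, not of reactions or of misclassified patients.

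**Trace of a drug first taken after the observation period**
1. *Before a late non-serious reaction, with no 24-hour reportable scenario.* The SAP counts it as exposure. Protocol 7.3.3.1 does not request it unless it treats an adverse event, and 9.1 sends nothing through the report form.
2. *Before a late serious reaction.* Protocol 9.1 requires concomitant medications, so it should be captured through case follow-up.
3. *After lack of efficacy.* This is 24-hour reportable, so the same follow-up applies. Protocol 9.4.1 also lists lack of efficacy as an adverse event, so a replacement drug could be read as adverse-event treatment under 7.3.3.1.
4. *Given to treat a reaction.* It is entered on the CRF, but normally starts on or after onset and so says little about the cause of that reaction. Because the cut-off is the last reaction, a drug treating an earlier event can count as exposure for a later one. Only patients with events have such entries.
5. *In a patient with no adverse event or reportable scenario.* It is not requested at all, and footnote a does not say which cut-off applies to a patient without a reaction.

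Lines 2 to 4 add later drug data mainly for patients with events, line 1 omits it for some patients with reactions, and line 5 omits it for patients without events. Missed exposure in line 1 could hide an association; event-only capture in lines 2 to 4 could create one.

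**The case against.** **Protocol 9.2 can be read as placing the 28 days inside the observation period.** On that reading, 7.3.3.1 already covers them. This stands as evidence that the definition is inconsistent, but it does not close the gap. Protocol 7.2.6 and SAP 2.1 both end the period on Day 10, SAP 8.2.3 ends it with treatment and adds 28 days separately, and 9.2 itself goes on to extend the reporting period beyond the end of observation.

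**Late non-serious reactions may scarcely enter the data.** Protocol 7.3.6 confirms adverse events only to the end of the observation period, the same limit as for drugs. This stands in part. Protocol 9.1 requires all non-serious events on the CRF and 9.2 applies its longer period to every listed event type, so how many are collected is unclear.

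**The other routes recover much of the later drug use.** They narrow the gap, but case by case and not for patients without a reportable event.

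**The analysis is exploratory.** SAP 4.1 says so, SAP 8.1.3 withholds risk ratios and differences for subgroups under 10, and Protocol 7.9 already admits missing chart data and limited confounder information. This limits the weight of the point. It does not justify coding uncollected data as 'absent'.

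A reader might go further and infer that a drug the patient was switched to is simply lost, that the bias runs towards finding no link with other drugs, and that the reaction is thereby left with AMEPAROMO. The documents support none of these. They describe no switch, and the routes above would capture some replacement drugs. Capture is unequal in ways that could push either way. SAP 6.1 defines a reaction by the investigator's judgement, so the exploratory table assigns no causality.

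**Conclusion.** The mismatch is real and should be corrected. Routine drug recording stops 28 days before the end of the window in which the SAP relates drugs to reactions (29 days in the SAP's Day 11 example), and the plan can then class an unrecorded drug as 'absent'. The consequence is unequal capture between patients with and without reactions, with bias of unknown direction, in an exploratory analysis. The main analysis items in Protocol 7.7 are not affected.

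The falling share of recorded days might suggest that the gap is longest for early stoppers. It is not: the gap is 28 days for a Day 3 stop and for a Day 10 completion, and only the ratio changes.

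This rests on reading the observation period as Protocol 7.2.6 defines it. False 'absent' status also requires that the patient took no concomitant drug earlier. The effect on results cannot be computed, because the documents give neither a rate of late reactions nor a rate of drug starts after treatment.

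**What to change.** 1. Reconcile the observation period across Protocol 7.2.6, 7.3.6 and 9.2 and SAP 8.2.3, so that drug recording, adverse-event collection and analysis refer to the same days.
2. In Protocol 7.3.3.1 and Table 1, record concomitant drugs for all patients, with or without a reaction, to the end of the SAP 8.2.3 window. The uncovered days then fall from 28 to 0; for a 10-day course, recording runs to Day 38.
3. In SAP 5.3 footnote a and the matching footnote used in 8.2.3.5, state the drug cut-off for patients without a reaction.
4. For patients already completed, limit the concomitant-drug factor in SAP 5.3 and the table in 8.2.3.5 to drugs and reactions within the recorded observation period, applied equally to patients with and without reactions. List later reactions separately as 'concomitant drugs not routinely collected'.

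Cost: one changed CRF instruction and slightly more transcription from the same chart. The fallback in item 4 needs SAP wording only, at the price of fewer reactions in an exploratory table.
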